# 7. Image Interpretation

# 7.1. C-acetate PET/CT Image Analysis

The low dose CT from the C-Acetate PET/CT scans will be reviewed by a trained radiology reader designated by the principal investigator. Any findings that may affect the clinical course of the subject will be reported to the patient's physician. The C-Acetate PET/CT data is not validated for clinical use; as such, results will not be reported.

C-Acetate PET/CT, Amyloid PET/CT and MRI images will be coregistered to allow template-based determination of regions of interest (ROI) on PET. We will obtain venous blood samples to calibrate an image-based arterial input function for the kinetic analysis.

Standardized uptake value ratio (SUVr), the ratio of regional to reference uptake, will be calculated with cerebellum as reference for both the C-Acetate and the amyloid PET/CT images. To account for atrophy, partial volume correction will be applied. Regional quantification will be performed using analysis software, such as Scenium (Siemens Medical Systems), PMOD (PMOD Technologies), or SPM (Wellcome Trust). Voxel based comparisons of PET/CT and MRI data may also be performed. We may also use graphical (Patlak) analysis, and with kinetic analysis using a two compartment model, which we have tested on other applications such as brain tumors   . Plasma CO2 will be estimated from venous samples, which will each be divided into two aliquots, one into acidic and the other into basic solution. Radioactivity in each aliquot will be counted with the difference in counts between acidic and basic used to calculate plasma CO2, which will be used in kinetic analysis of acetate binding.

Optimal quantification of acetate binding will be the simplest model that shows strong correlations between acetate binding and amyloid SUVR. Acetate binding and amyloid SUVR will be analyzed using PMOD for modeling and static uptake estimates and Statistical Parametric Mapping using T1 MRI for coregistration and template-based regional segmentation. We will compare and correlate amyloid and acetate quantification using both Pearson's correlation and non-parametric Spearman's correlation.

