# 3. Study Design

Subjects will be part of one of the following cohorts:

- Cohort 1:Patients with Mild Cognitive Impairment (MCI) (up to 14) will be recruited primarily from the Penn Memory Center (PMC). Clinical diagnostic criteria (described in further detail in Study Procedures section) will be used to identify subjects who are meet criteria for amnestic MCI.
- Cohort 2: Normal control subjects in the same age range (up to 6) will be recruited from a current ongoing study investigating neuroinflammation in late life depression and healthy controls, from the control group in which all subjects receive MRI and LP (IRB 819654) and from the PMC research cohort.
- Cohort 3: Cognitively normal subjects with a positive Amyloid PET (up to 5) may be recruited through other ongoing studies or PMC research cohort

Screening assessments may take place over several days and may include demographic information, neurocognitive testing, with focus on language and visuospatial/ visuoperceptual measures; if available within 6 months of the study entry these tests may not be repeated. Amyloid brain PET/CT scan isrequired for Cohort 1 and Cohort 3 only, subjects in Cohort 2 may have an Amyloid PET that has been done as part of standard care or another study but this is not required for entry into Cohort 2- In order to reduce costs, subjects may be recruited from other studies that perform amyloid PET/CT (typically with F-florbetaben or F-florbetapir) or have this test performed clinically. The CMS coverage

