with evidence development IDEAS amyloid PET/CT study starts recruitment February 2016, providing Medicare reimbursement for clinical amyloid PET/CT scans for the first time; Penn will be a site for this study and we anticipate that many MCI patients being considered for this experimental C-Acetate imaging protocol will qualify to undergo clinical Amyloid PET/CT as part of the IDEAS trial (IRB # 824052). Amyloid PET/CT scans should be completed within 6 months prior to the C-Acetate PET/CT. If a subject has not undergone an Amyloid brain PET/CT as part of IDEAS or clinically then they will be asked to undergo a research Amyloid brain scan after they have consented for this study. If it is done as part of this research study the FDA approved radiotracer [18F]Florbetaben (Neuraceg) will be used according to the standard Penn imaging procedure. When available, an Amyloid brain PET/CT scan will be reviewed by an investigator or designee prior to scheduling the C-Acetate PET/CT scan. For Cohort 1, if the Amyloid PET/CT scan is deemed to be negative then the subject will be considered non-evaluable and will be withdrawn from the study. Cognitively normal subjects will be assigned to Cohort 2 (negative amyloid PET) or 3 (positive amyloid PET); cognitively normal subjects can also be included in Cohort 2 with negative CSF biomarkers. Non-evaluable subjects will be replaced in the study enrollment total.

If the subject has undergone a brain MRI within 6 months of C-Acetate PET/CT it may meet the study requirements for MRI imaging; the scan will be reviewed by a study physician to determine whether it can be used for the purposes of this study. If the subject does not have a Brain MRI that is deemed acceptable within 6 months of C-Acetate PET/CT they will be asked to undergo a research Brain MRI after they have consented for this study.

Subjects who qualify for the study will undergo an C-Acetate PET/CT imaging session after completing the screening requirements. Patients that meet the eligibility criteria will be approached about study participation regardless of race or ethnic background.

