- physician to determine if the MRI can be used for the purposes of the study, this may occur prior to consent and enrollment in this study.
- 6. Amyloid brain PET/CT scan (required for Cohort 1 and Cohort 3) In order to reduce costs, subjects may be recruited from other studies that perform amyloid PET/CT (typically using F-florbetaben or F-florbetapir. The CMS coverage with evidence development IDEAS amyloid PET/CT study starts recruitment February 2016, providing Medicare reimbursement for clinical amyloid PET/CT scans for the first time; Penn will be a site for this study and we anticipate that many patients being considered for this experimental C-Acetate imaging protocol will qualify to undergo clinical Amyloid PET/CT as part of the IDEAS registration trial (IRB 824052). Amyloid PET/CT scans should be completed within 6 months of study enrollment. If a subject has not undergone an Amyloid brain PET/CT as part of IDEAS or clinically then they will be asked to undergo a research Amyloid brain scan after they have consented for this study. If it is done as part of this research study the FDA approved radiotracer [18F]florbetaben (Neuraceq) will be used according to the standard Penn imaging procedure. For Cohort 1 and Cohort 3, the Amyloid brain PET/CT scan will be reviewed by an investigator or designee prior to scheduling the C-Acetate PET/CT scan, for subjects in Cohort 2 if an Amyloid PET is available it will be reviewed, however, it is not required for participation in Cohort 2.. If the Amyloid PET/CT scan is deemed to be negative then the subject will be considered non-evaluable and will be withdrawn from the study. Non-evaluable subjects will be replaced in the study enrollment total.

Baseline assessments: may be performed the same day as screening assessments or on a separate day within 90 days of the C-Acetate PET/CT, including the day of that study.

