### 8.3. Subject Population(s) for Analysis

The primary analysis population will consist of age matched cohorts of amnestic MCI patients and normal controls. Patients will be recruited from the clinical practices of Penn Memory Center, Frontotemporal Lobar Degeneration Center, or other clinics of the University of Pennsylvania Health System. All subjects with an C-acetate PET/CT will contribute to the primary analysis.

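### Acetate quantification is not masked to cohort, and Section 7.1 brings the amyloid scan into the image workflow before acetate regions are set

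*Combined protocol and SAP*

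**What the plan says.** - **Workflow.** Section 7.1 takes the acetate scan together with the other images: "Amyloid PET/CT and MRI images will be coregistered to allow template-based determination of regions of interest (ROI) on PET". Later in the same section the anatomical basis is the MRI, "using T1 MRI for coregistration and template-based regional segmentation".
- **Amyloid scan known beforehand.** Section 6.1: "For Cohort 1 and Cohort 3, the Amyloid brain PET/CT scan will be reviewed by an investigator or designee prior to scheduling" of the acetate scan.
- **Controls.** For amyloid PET in controls, Section 3 says "this is not required for entry into Cohort 2", and "cognitively normal subjects can also be included in Cohort 2 with negative CSF biomarkers".
- **Discretion.** Section 7.1 gives software as an open list of three packages, names no partial volume correction method, and makes Patlak and two-compartment analyses optional. For kinetics: "We will obtain venous blood samples to calibrate an image-based arterial input function for the kinetic analysis". Section 6.2 lets an investigator omit venous sampling.
- **Model choice.** Sections 7.1 and 8.2 choose the acetate measure by simplicity and by the strength of its correlation with amyloid SUVR, with no threshold for strong.
- **Primary variable and population.** Section 7.2 lists regional acetate SUVR among the primary analysis variables. Section 8.3: "The primary analysis population will consist of age matched cohorts of amnestic MCI patients and normal controls", and every subject with an acetate "PET/CT will contribute to the primary analysis".
- **Masking.** No section addresses it for the acetate analysis. Section 10.1 provides for ID numbers and/or initials in analysis data sets, as a privacy measure.

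**The concern.** The primary objective compares amyloid-positive MCI subjects with amyloid-negative controls, so within that contrast amyloid status separates the two groups completely. An analyst who has the amyloid image open while checking the registration of the acetate scan can usually tell which group the subject belongs to. An analyst who finds no amyloid scan can infer a control, because only Cohorts 1 and 3 must have one.

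Template regions limit what an operator can do, but they leave open whether to accept or repair a registration or segmentation, which partial volume correction to apply, and which package or model to use. When such choices are made with the group in view and the hoped-for direction known, small shifts can accumulate on one side. The study is unrandomised and has at most six controls, so little averages this out. Section 8.1 also intends the pilot to inform the sample size of a larger study, so a biased difference would carry forward.

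**Working it through.** **1. Can the analyst see the group?** Setting the sections side by side:

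| Subject | Amyloid scan in the workflow | What it reveals |
|---|---|---|
| MCI (Cohort 1) | Required; negatives are withdrawn | Positive image: Cohort 1 or 3 |
| Control, entered on PET | Present | Negative image: control |
| Control, entered on CSF | May be absent | Absence points to a control |
| Cohort 3 | Required | Positive image: Cohort 1 or 3 |

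For the primary contrast (Cohort 1 against Cohort 2), image appearance or absence is enough. Study IDs do not hide this.

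**2. Does acetate quantification need the amyloid image?** No. Section 7.1 uses the T1 MRI for coregistration and regional segmentation, and the acetate SUVR is a ratio to cerebellum. Amyloid images are needed later, for the correlations and for the comparison of voxels by amyloid level. Reordering the steps loses nothing.

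**3. Which discretionary steps reach the primary variable?** Registration and segmentation checks, partial volume correction and software reach the SUVR. The input function and venous samples do not; they matter only if a kinetic measure is used.

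**4. Leverage.** A change of x points in one control's value moves the control mean by x/6. The same change in one MCI subject moves that mean by x/14. Lowering the control mean by 5 points takes 6 × 5 = 30 points in total across the six controls.

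**5. Illustration of sensitivity.** The documents give no size for analyst effects, so shifts of 2, 5 and 10 points are assumed. Other inputs are 14 and 6 subjects (Section 8.1), the stated 20% precision read as an SD (assumption), no true difference, and a pooled t-test at 0.05 (assumption; Section 8 names no test for this comparison).

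The plan's own figure does not reproduce on these inputs. At 80% two-sided power the detectable difference is 20% × (1.960 + 0.842) × √(1/14 + 1/6) = 27.3%, against the stated 15%. That is a separate matter, and the 15% is not used as a yardstick here.

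Standard error of the difference: 20 × √(1/14 + 1/6) = 20 × 0.488 = 9.76 points, with 14 + 6 − 2 = 18 degrees of freedom. A downward shift b in all control values gives noncentrality b/9.76:

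| Shift b (points) | b/9.76 | Type I error, one-sided | Two-sided |
|---|---|---|---|
| 0 | 0 | 5.0% | 5.0% |
| 2 | 0.20 | 7.4% | 5.4% |
| 5 | 0.51 | 12.5% | 7.7% |
| 10 | 1.02 | 25.5% | 16.3% |

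These figures show how sensitive the comparison is. They do not estimate bias in this study.

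**The case against.** The strongest reply is that the plan is silent on masking and does not require anyone to be unmasked. Coregistration is a spatial step that can be automated or run on coded files. The person who reviews the amyloid scan for eligibility is not said to be the person who quantifies acetate. Outputs are template-derived numbers, not visual reads, and this is a pilot. All of that stands. It rules out the reading that quantification is unblinded by construction, but it does not supply masking.

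Other inferences a reader might draw also go too far:

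- **Every acetate scan is registered to the amyloid scan that defines the group.** Controls who enter on CSF may have no amyloid scan, and groups are defined by cognition as well as amyloid: Cohorts 1 and 3 are both positive.
- **Quality exclusions could be steered.** One might delete a control lying 2 SD (40%) above the other five, which lowers the control mean by 40/6 = 6.7 points, or 44% of 15%. The arithmetic is right, but Section 8.3 keeps every subject with an acetate scan, and the adequate-quality wording in Section 4 covers amyloid PET and MRI. What remains is the lack of a rule for an acquired acetate scan that cannot be quantified.
- **The harm could never be undone.** Section 1.3 stores the research images on PACS, so masked re-quantification would remain possible.

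**Conclusion.** The point holds in a limited form. The plan states a joint workflow that can expose the group, specifies no masking of acetate quantification, and leaves several steps that affect the primary SUVR to discretion, in a comparison of at most 14 with at most 6. This is avoidable exposure to analyst bias; it is not evidence that bias will occur. Its size cannot be derived from the documents. The type I error figures rest on an assumed SD of 20%, an assumed t-test and assumed shifts applied to every control.

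The change is worth making because the plan's own MRI-based segmentation already makes masked quantification feasible.

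**What to change.** In Section 7.1:

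1. Label acetate PET and MRI files by study code, without cohort.
2. Quantify acetate from the acetate PET and T1 MRI alone, with one pipeline for all subjects (software, registration and segmentation checks, partial volume correction). Where a kinetic measure needs venous counts, supply them under the same code.
3. Lock the cerebellum-referenced SUVR named in Section 7.2, every candidate kinetic measure, and any judgement that a scan cannot be quantified.
4. Only then link cohort and register the amyloid images.
5. Apply the amyloid-correlation rule for model choice after that, to the locked values.
6. Log any later change with its reason.

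**Cost.** Files must be coded and amyloid registration becomes a separate second step. The same analyst and software can be used, with no extra subjects or scans.

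**Limits.** Atrophy visible on the MRI may still hint at MCI. The model-choice rule still uses amyloid data by design; the new order only stops it from influencing how the individual acetate values are produced.

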#### 7.2. Measurement of Effect

This protocol is designed to develop relationships between parameters determined from an C-Acetate PET/CT imaging biomarker study and ones derived from amyloid PET/CT, MRI, laboratory biomarker assays, and neurocognitive testing.

The primary analysis variables for the study are:

- C-Acetate PET/CT SUVR regional quantification
- Amyloid PET/CT SUVR
- Statistical Parametric Mapping segmentation of MRI

Secondary analysis variables are:

• Levels of IL-6, IL-1 and TNFα in CSF

• Neurocognitive test results (tests detailed elsewhere in this document)

### 8. Statistical Plan

### 8.1. Sample Size Determination

The primary objective will be to evaluate whether C-acetate uptake is increased in amyloid positive Mild Cognitive Impairment (MCI) subjects compared to amyloid negative healthy controls. With a sample size of 14 MCI and 6 normal controls, assuming 20% precision, we estimate we could detect a difference of 15%; with a smaller sample of 8 MCI subjects and 4 controls, we estimate that we could detect a difference of 30%, However, this is a pilot study which will allow us to determine feasibility and estimate sample size for a future larger study.

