# 2. Study Objectives

## 2.1. Primary Objective

 Evaluate whether C-acetate uptake is increased in amyloid positive Mild Cognitive Impairment (MCI) subjects compared to amyloid negative healthy controls

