#### 8.2. Statistical Methods

Optimal quantification will be the simplest model that shows strong correlations between acetate binding and amyloid SUVR. C-Acetate binding and amyloid SUVR will be analyzed using PMOD for modeling and static uptake estimates and Statistical Parametric Mapping using T1 MRI for coregistration and template-based regional segmentation. We will compare and correlate amyloid and acetate quantification using both Pearson's correlation and non-parametric Spearman's correlation.

The expected positive correlation between acetate binding and CSF cytokine levels will be evaluated. Global, regional and voxel based correlations will be performed between acetate uptake and amyloid PET SUVR from MCI subjects and cognitively normal subjects with a positive Amyloid scan. Acetate binding in voxels with amyloid SUVR below, between 100-125%, or above 125% of previously validated thresholds will also be compared.

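### The two detectable differences in Section 8.1 (15% with 14 vs 6, 30% with 8 vs 4) cannot come from one set of assumptions: the step should be about 1.3-fold, not 2-fold

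*Combined protocol and SAP*

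**What the plan says.** The primary objective (Section 2.1) is to find out whether acetate "uptake is increased in amyloid positive Mild Cognitive Impairment (MCI) subjects compared to amyloid negative healthy controls". Section 8.1 is the only place that says how large a difference this comparison could show. For the planned cohorts: "With a sample size of 14 MCI and 6 normal controls, assuming 20% precision, we estimate we could detect a difference of 15" percent. After a semicolon it adds: "with a smaller sample of 8 MCI subjects and 4 controls, we estimate that we could detect a difference of 30" percent. The variability term, "assuming 20% precision", is not defined. No alpha, sidedness, power or test is given.

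Section 8.2 does not fill the gap. It describes correlations ("We will compare and correlate amyloid and acetate quantification using both" Pearson and Spearman coefficients) and a comparison of voxels grouped by amyloid threshold, but names no test for MCI versus controls. Section 8.1 closes by calling the study a pilot that will inform feasibility and the size of a larger trial.

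**The concern.** The sentence reads as one calculation done for two sample sizes. Cutting the groups from 14 and 6 to 8 and 4 is a moderate reduction, yet the detectable difference doubles. Detectable differences scale with the standard error, so halving sensitivity through sample size alone would take roughly a fourfold cut in the groups. Either one figure is wrong or the two rest on different inputs that are not disclosed.

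What is at stake is how the primary result will be read. If 14 vs 6 really detects 15%, a null result argues against a 15% increase. If it detects only 23% or more, a null result says little about 15%.

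**Working it through.** **Inputs from Section 8.1:** 14 vs 6 with 15%; 8 vs 4 with 30%; 20% for variability. **Assumed, because not stated:** a two-sample comparison of means, with the same SD, alpha, sidedness and power for both figures.

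**Step 1. Ratio of the two figures, with no value assumed for the SD.** The detectable difference is D = k × SD × √(1/n₁ + 1/n₂), where k depends on alpha, power and degrees of freedom. A common SD cancels from the ratio.

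- 14 vs 6: √(1/14 + 1/6) = 0.488
- 8 vs 4: √(1/8 + 1/4) = 0.612
- Standard error ratio: 0.612 / 0.488 = 1.255
- If the groups have different SDs, the standard error ratio lies between √(6/4) = 1.22 and √(14/8) = 1.32.
- With noncentral-t values for k (18 and 10 degrees of freedom, 5% alpha, 80% power), the ratio of detectable differences is 1.298 one-sided and 1.317 two-sided. Over alpha 1–20%, one- or two-sided, and power 50–90%, it is 1.26 to 1.37.
- Ratio stated in the plan: 30 / 15 = 2.0

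**Step 2. What each figure implies for the other.**

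- From 15% at 14/6: 15 × 1.255, 1.298 or 1.317 = 18.8%, 19.5% or 19.8% at 8/4.
- From 30% at 8/4: 30 divided by the same factors = 23.9%, 23.1% or 22.8% at 14/6.
- SD needed at 5% alpha and 80% power by t-test: for the 15% figure, 11.9% one-sided or 10.4% two-sided; for the 30% figure, 18.3% or 15.8%. One SD cannot serve both.

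**Step 3. Attempt to reproduce the figures with SD = 20% (an assumption).** The standard errors are 20 × 0.488 = 9.76 points and 20 × 0.612 = 12.25 points.

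| Detectable difference | 14 vs 6 | 8 vs 4 |
|---|---|---|
| Plan | 15% | 30% |
| Normal, one-sided 5%, 80% power | 24.3% | 30.5% |
| t-test, one-sided 5%, 80% power | 25.2% | 32.7% |
| Normal, two-sided 5%, 80% power | 27.3% | 34.3% |
| t-test, two-sided 5%, 80% power | 28.9% | 38.1% |
| t-test, one-sided 10%, 80% power | 21.2% | 27.2% |
| t-test, one-sided 20%, 80% power | 16.6% | 21.0% |

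The 30% figure is close to the one-sided normal approximation. The 15% figure is not close to any row at 5% alpha. Error rates loose enough to bring 14/6 near 15% pull 8/4 down to 21%.

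In standard errors, the plan's figures are 15 / 9.76 = 1.54 and 30 / 12.25 = 2.45, so they cannot share one k. At SD 20%, an observed difference at 14/6 would have to exceed 16.9 points to be significant even at one-sided 5%.

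**Step 4. Consequences at SD 20% (t-test, 5% alpha).** Power for a true 15% difference at 14/6 is 43% one-sided and 31% two-sided. Power for 30% at 8/4 is 74% and 60%. The expected 95% confidence interval half-width is ±20.5 points at 14/6 and ±27.3 points at 8/4.

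**The case against.** The strongest reply is that the ratio argument needs alpha, power, sidedness and test to be the same for both figures, and Section 8.1 states none of them. The words "assuming 20% precision" also stand only in the first half of the sentence. That condition is real. But the sentence changes only the sample size and discloses no other change. If the inputs did differ, the reader has to be told, and the correction is the same.

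A second reply is that 1.3 is not universal. Other methods at 5% alpha give more: about 1.35–1.41 on the log scale with a CV of 20% and 80–95% power, about 1.29–1.38 for a Wilcoxon test, and up to about 1.5 when the degrees of freedom come from the smaller group alone. A Welch test with nearly all the variance in the controls gives 1.39 one-sided or 1.48 two-sided at 80% power; at two-sided 1% alpha that limiting case reaches 1.76. So the size of the mismatch depends on the method. None of these variants reaches 2.0, and stricter alpha moves 14/6 further from 15% at SD 20%.

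Third, everything in Steps 3 and 4 depends on reading 20% as the between-subject SD. That is correct: without that reading one can say that the figures conflict, but not which is wrong.

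Finally, this is a pilot, both figures are offered as estimates, and no decision rule uses them. That limits the consequence. It does not make the two numbers agree.

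**Conclusion.** The concern holds: Section 8.1 is wrong as written. Under one common set of inputs, the stated 2.0-fold step compares with 1.25 (normal) to 1.32 (t-test, two-sided 5%), a mismatch of about 1.5- to 1.6-fold. Less usual methods narrow that gap but do not close it. This conclusion needs no value for the SD, only that both figures share the same SD, test, alpha, sidedness and power.

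If 20% is the between-subject SD, with 5% alpha and 80% power, the 15% claimed for the planned sample is too favourable by a factor of 1.6 (24.3 / 15) to 1.9 (28.9 / 15). The 30% is too favourable by about 2% (30.5 / 30) to 27% (38.1 / 30). The point should be fixed, but it does not threaten the design.

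**What to change.** Keep the sample size and rewrite Section 8.1 to:

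- say what the 20% is (between-subject SD, or measurement error) and on what evidence it rests;
- name the test for MCI versus controls, with alpha, sidedness and power, and carry the same test into Section 8.2;
- recompute both detectable differences from those inputs;
- give the expected 95% confidence interval half-width, which suits a pilot better than a detectable difference.

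As a worked example, with a between-subject SD of 20% and a t-test at 5% alpha and 80% power, the pair would be about 29% (14 vs 6) and 38% (8 vs 4) two-sided, or 25% and 33% one-sided. The half-width for 14 vs 6 would be about ±20 points. If a smaller SD is intended, justify it and derive both figures from it.

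The cost is the text of Section 8.1 and a matching line in Section 8.2, with no extra subjects or procedures. At least one stated figure will change, and under the 20% SD reading the stated sensitivity becomes less favourable.
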